5.12 Health Outcomes/Quality-of-Life Analyses

The description and derivation of the health outcomes/QoL analyses are described in [Table KGBP.5.4](#). For categorical parameters, the number and percentage of patients in each category will be presented, as well as a 90% Wilson-Score confidence interval for the percentage. For continuous parameters, descriptive statistics will include n (number of patients), mean, standard deviation, Q1, median, Q3, minimum, and maximum. These summaries will be provided for the data as-observed and after implementation of LOCF and MCMC-MI imputation as described in Sections 5.4.2 and 5.4.3. Patient-Reported Outcomes Information System and DLQI/CDLQI will be reported by clinic visit.

5.13 Safety Analyses

The planned analyses of safety data will be performed with an intent to maintain consistency with compound-level standard safety analyses. These standards are based on internal standards which were informed by CDISC standards, regulatory guidance (eg, FDA Clinical Review Template), and cross-industry standardization efforts (eg, PhUSE white papers from the Standard Analyses and Code Sharing Working Group provided in the PhUSE Computational Science Deliverables Catalog [WWW]).

The laboratory (including hormone), vital sign (including growth), and immunogenicity safety summaries will be based on the safety population. The extent of exposure and AE tables will be based on the safety population.

These analysis populations are fully defined in Table KGBP.5.1.

Not all displays described in this section will necessarily be included in the CSRs. Any display described and not provided in the CSR would be available upon request. Not all displays will necessarily be created as a “static” display. Some may be incorporated into interactive display tools instead of or in addition to a static display. Any display created interactively will be included in the CSR if deemed relevant to the discussion.

5.13.1. Extent of Exposure

A by-patient listing of exposure duration with the number of active injections and total dose will be provided for the Safety Population.

The duration of exposure will be calculated as:

Duration of exposure (days)=

Date of last visit (scheduled or unscheduled) in the Treatment Period –

Date of first dose+1

The number and percentage of patients in each of the following categories will be included in the summaries:

>0 , ≥ 7 days, ≥ 14 days, ≥ 30 days, ≥ 60 days, ≥ 90 days, ≥ 112 days, ≥ 120 days, ≥ 168 days. Note that patients may be included in more than 1 category.

The summaries will also include the following information:

- total exposure in patient years, calculated as:

Total exposure in patient years

$$= \frac{\text{Sum of duration of exposures for all patients in treatment group}}{365.25}$$

- mean and median total dose; total dose (in mg) is calculated by the number of active injections taken multiplied by 250.
- Total number of injections received will be derived from the *Exposure as Collected* eCRF page and on the *Exposure as Collected: Missed Injections at Home* eCRF page.

5.13.2. Adverse Events

A TEAE is defined as an event that first occurred or worsened in severity after baseline (i.e., AEs with an onset date on or after the date of the first injection of study drug). The MedDRA lowest level- term will be used in the treatment-emergent computation. The maximum severity for each lowest -level term during the baseline period will be used as baseline. The treatment period will be included as post-baseline for the summaries. For events with a missing severity during the baseline period, the events will be treated as ‘mild’ in severity for determining treatment-emergence. Events with a missing severity during the postbaseline period will be treated as ‘severe’, and treatment-emergence will be determined by comparing to baseline severity. For events occurring on the day of first taking study medication, the events will be assumed to be posttreatment.

The planned summaries for AEs are provided in [Table KGBP.5.5](#) and are described more fully in compound-level safety standards and in the AE-related PhUSE white paper [Analysis and Displays Associated with Adverse Events: Focus on Adverse Events in Phase 2-4 Clinical Trials and Integrated Summary Document (PhUSE 2017)].

Summary tables will be presented for the safety population. Summary tables will include the number and percentage of patients reporting an event. For events that are gender-specific (as defined by MedDRA), the number of participants at risk will include only patients from the given gender.

Table KGBP.5.5. Summary Tables/Listings Related to Adverse Events

Summaries	Population
Overview of AEs	Safety
Summary of TEAEs by PTs	Safety
Summary of TEAEs by PTs within SOC	Safety
Summary of TEAE PTs by maximum severity	Safety
Summary of SAEs by PT within SOC	Safety
Summary of AEs leading to treatment discontinuation by PT with SOC	Safety

Summary of TEAEs possibly related to study drug by PTs within SOC	Safety
Summary of treatment-emergent adverse events – facial dermatitis follow-up form	Safety
Listing of SAEs (including Death)	Safety
Listing of primary AEs leading to study treatment discontinuation	Safety
Listing of TEAEs	Safety

Abbreviations: AE = adverse event; PT = Preferred Term; SAE = serious adverse event; SOC = System Organ Class; TEAE = treatment-emergent adverse event.

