## 6.7. Treatment of Overdose

For this study, any dose of lebrikizumab greater than 500 mg (baseline and Week 2) and 250 mg Q2W (Week 4 and beyond) will be considered an overdose.

Sponsor does not recommend specific treatment for an overdose.

In the event of an overdose, the investigator/treating physician should:

- Contact the medical monitor immediately.
- Evaluate the participant to determine, in consultation with the medical monitor, whether study intervention should be interrupted or whether the dose should be reduced.
- Closely monitor the participant for any AE/SAE and laboratory abnormalities until lebrikizumab can no longer be detected systemically (at least 18 weeks).

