## 8.2. Safety Assessments

Planned time points for all safety assessments are provided in the SoA.

The routine safety assessments include physical examinations, clinical safety laboratory tests (including hematology and chemistry), and collection of vital signs and spontaneously reported AEs. The study design includes a Post-treatment Follow-Up Period with at least 1 study visit for safety assessments.

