### **9.3.5. Safety Analyses**

All safety data will be descriptively summarized using the safety population.

TEAEs are defined as AEs that first occurred or worsened in severity after the first dose of study treatment. The number and percentage of participants who experienced at least 1 TEAE will be summarized using the most current version of MedDRA (Medical Dictionary for Regulatory Activities) by system organ class (or body system) and by each preferred term. SAEs and AEs that lead to discontinuation of study intervention will also be summarized.

All clinical laboratory results will be descriptively summarized. Individual results that are outside of normal reference ranges will be flagged in data listings. Quantitative clinical hematology, chemistry, and urinalysis variables obtained at the baseline to postbaseline visits will be summarized as changes from baseline. Categorical variables, including the incidence of abnormal values and incidence of AEs of special interest, will be summarized by frequency and percentage of participants in corresponding categories. Shift tables might be presented for selected measures.

Observed values and changes from baseline (predose or screening if missing) for vital signs and physical characteristics will be descriptively summarized by time point.

The SAP may include additional safety analyses if needed.

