5.13.2.2. Deaths, Other Serious Adverse Events and Other Notable Adverse Events

The number and percentage of patients reported with an SAE during the treatment period will be summarized using MedDRA PT. A listing of SAEs will be provided.

The number and percentage of patients who permanently discontinued from study treatment due to an AE (including AEs that led to death) during the treatment period will be summarized using MedDRA PT. Events will be ordered by decreasing frequency.

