5.13.6.1. Hepatic Safety

Hepatic labs include alanine aminotransferase (ALT) aspartate transaminase (AST), total bilirubin (TBL), and serum alkaline phosphatase (ALP).

Table KGBP.5.8. Summary Tables/Figure Related to Hepatic Safety

Summaries	Population
ALT and AST: The number and percentage of subjects with a measurement greater than or equal to 3 times (3X), 5 times (5X), and 10 times (10X) the performing lab ULN during the treatment period for all subjects with a postbaseline value and for subsets based on various levels of baseline value	Safety
TBL and ALP: The number and percentage of subjects with a measurement greater than or equal to 2 times (2X) the performing lab ULN during the treatment period will be summarized for all subjects with a postbaseline value and for subsets based on various levels of baseline value	
Plot of maximum postbaseline ALT vs. maximum postbaseline total bilirubin	Safety

Abbreviations: ALP = serum alkaline phosphatase; ALT = alanine aminotransferase; AST = aspartate transaminase; TBL = total bilirubin; ULN = upper limit of normal.

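### The SAP's SAE and hepatic threshold tables, and on the natural reading its TEAE tables, stop at the end of the treatment period; no incidence table covers safety follow-up, and the documents disagree on the TEAE window

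*SAP*

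**What the plan says.** **Windows in the SAP.** SAP 4.1 lists the treatment period (Visits 2 to 9, 24 weeks) and the safety follow-up (Visit 801) as separate periods. For adverse event summaries, 5.13.2 says "The treatment period will be included as post-baseline for the summaries". For serious events, 5.13.2.2 says "The number and percentage of patients reported with an SAE during the treatment period will be summarized using MedDRA PT", and it sets the same limit for AEs leading to treatment discontinuation. In 5.13.6.1 the ALT/AST threshold row counts multiples of "the performing lab ULN during the treatment period for all subjects with a postbaseline value"; the bilirubin/ALP row has the same limit. No incidence table for follow-up events is described.

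**Data collected.** The protocol's Schedule of Activities (1.3) marks AEs, hematology and chemistry at Visit 801. Section 8.3.1 collects AEs and SAEs until participation ends. Section 8.2 says "The study design includes a Post-treatment Follow-Up Period with at least 1 study visit for safety assessments". SAP 5.16 places the final lock after that follow-up.

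**Definitions of a treatment-emergent event.** Protocol 9.3.5: "TEAEs are defined as AEs that first occurred or worsened in severity after the first dose of study treatment", with no end date, and the same section says all safety data will be summarized. The SAP's own definition in 5.13.2 is also open-ended: "AEs with an onset date on or after the date of the first injection of study drug". The glossary in protocol Appendix 11, however, requires the event to emerge within a defined treatment period.

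**The concern.** The study's title and its stated design purpose (protocol 4.1) put safety beside efficacy, and the follow-up visit exists to collect safety data. A table that stops at the end of the treatment period gives no incidence for later infections, conjunctivitis or liver test elevations. A listing of such events has no denominator and no rate.

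The wording also leaves programming open. One programmer could follow the open-ended TEAE definition and count events to Visit 801. Another could follow the sentence on the post-baseline period and stop at Week 24. Both could cite SAP 5.13.2.

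**Working it through.** **1. Reproduce the plan's own timing.** Inputs: last scheduled dose at Week 20 for Week 16 responders and Week 22 for inadequate responders (protocol 6.1); follow-up visit 12 weeks after the last dose (SAP 4.1); screening up to 30 days (protocol 4.1).

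- Inadequate responders: 22 + 12 = Week 34, the week stated in SAP 4.1.
- Responders: 20 + 12 = Week 32.
- Longest participation: 34 + 30/7 = 38.3 weeks, against the planned 38 weeks in the protocol synopsis.

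The timing reproduces.

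**2. Share of a completer's time outside the window.** Formula: (Visit 801 week − 24) / Visit 801 week.

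- Responders: (32 − 24)/32 = 8/32 = 25%.
- Inadequate responders: (34 − 24)/34 = 10/34 = 29%.

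**3. Patient-years outside the window.** Formula: number with Visit 801 × weeks × 7 / 365.25. N = 95 (protocol 4.1), with no dropout. SAP 4.1 says participants who enter Continued Access skip Visit 801; their share is not given, so it is varied as an assumption. The treatment period itself gives 95 × 24 × 7 / 365.25 = 43.7 patient-years.

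| Assumed share entering Continued Access | All responders (8 weeks) | All inadequate responders (10 weeks) | Share of total time |
|---|---|---|---|
| 0% | 14.6 | 18.2 | 25–29% |
| 50% | 7.3 | 9.1 | 14–17% |
| 90% | 1.5 | 1.8 | 3–4% |

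**4. Early discontinuers.** Protocol 6.6 offers Continued Access only after completion of Week 24, so this group cannot enter it; protocol 7.1 sends them to an early discontinuation visit and post-treatment follow-up. If the treatment period is assumed to end at the last dose, the share outside the window is 12 / (last dose week + 12):

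- last dose at Week 4: 12/16 = 75%
- last dose at Week 16: 12/28 = 43%

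If it ends instead at an early discontinuation visit two weeks after the last dose (also an assumption), the shares are 10/16 = 62.5% and 10/28 = 36%.

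**5. Which outputs carry the limit.**

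| Output | Window as written |
|---|---|
| TEAE tables, including AESI tables built on TEAEs (5.13.2, 5.13.6.3, 5.13.6.4) | Treatment period by natural reading; the word *only* does not appear |
| SAE incidence by preferred term (5.13.2.2) | Treatment period, explicit |
| ALT/AST and bilirubin/ALP thresholds (5.13.6.1) | Treatment period, explicit |
| SAE listing; infection and conjunctivitis listings | No limit stated |
| Laboratory shift and treatment-emergent tables (5.13.3) | Post-baseline, no treatment-period limit |
| ALT–bilirubin plot (5.13.6.1) | Post-baseline, no treatment-period limit |
| Registry SAE counts (5.18) | All SAEs, treatment-emergent or not |
| Registry non-serious AEs (5.18) | Only if treatment-emergent |

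**The case against.** A reader might infer that the SAP simply contradicts the protocol's TEAE definition. The documents do not support that: the protocol has two definitions, and the one in Appendix 11 agrees with the SAP's treatment-period wording. What stands is an inconsistency among protocol 9.3.5, protocol Appendix 11 and SAP 5.13.2. Section 9.3.5 is the section on safety analyses and Appendix 11 is a glossary, but neither is said to prevail.

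A reader might also infer that follow-up events vanish from all reporting. They do not. SAP 5.13.2.2 says "A listing of SAEs will be provided" without a time limit, the registry counts SAEs with numbers at risk, and the infection and conjunctivitis listings, laboratory shift tables and ALT–bilirubin plot are not tied to the treatment period. The discontinuation table loses essentially nothing, since a participant already off treatment cannot stop it. The gap is in the CSR incidence tables. It can also make the CSR and registry SAE counts differ, although 5.18 calls for consistent reporting.

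It is tempting to say the protocol states that drug is present throughout follow-up. The 18-week figure in protocol 6.7 is an overdose monitoring instruction and says nothing about Visit 801 after planned dosing. Persistence is at most an inference.

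Finally, the SAP defers AE display details and AESI rules to compound-level safety standards that are not among the documents. Those standards may define the window. This lowers confidence for the TEAE and AESI tables, but it does not remove the explicit limits in 5.13.2.2 and 5.13.6.1.

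**Conclusion.** The concern holds in a limited form. As written, follow-up events are left out of the SAE incidence table and the hepatic threshold tables, and on the natural reading also out of the TEAE and AESI incidence tables. No follow-up table replaces them, and the documents disagree on where the TEAE window ends.

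The 25% to 29% figure applies only to completers who have Visit 801; it is not the loss for every participant. The total of 14.6 to 18.2 patient-years is an upper bound for 95 participants, with no dropout and nobody in Continued Access. It shrinks in proportion to Continued Access entry, to 1.5 to 1.8 at an assumed 90%. Early discontinuers are the most affected, at about 43% to 75% of observed time if the treatment period ends at the last dose. Protocol 7.2 expects discontinuation to be uncommon, so they may be few, but they include anyone stopped for an adverse event.

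The documents give no event rate for follow-up, so the number of events left out cannot be stated. The primary endpoint is unaffected. This is a worthwhile, inexpensive improvement to the safety reporting.

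**What to change.** In SAP 5.13.2, 5.13.2.2 and 5.13.6.1, state the end of the post-baseline window explicitly and reconcile it with protocol 9.3.5 and protocol Appendix 11, so that one TEAE definition governs. Keep the treatment-period tables and add parallel TEAE, SAE, AESI and hepatic threshold tables covering first dose through Visit 801 or end of participation. State in those tables how participants who enter Continued Access are handled, since they have no Visit 801.

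The cost is a short wording change and one extra set of tables. The data are already collected and already in the final lock. Reported event percentages may be slightly higher in the longer window.

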5.13.2.1. Common Adverse Events

The percentages of patients with TEAEs will be summarized using MedDRA PT for the common TEAEs (occurred in $\geq 1\%$ before rounding in any column in the table).

5.13.2.2. Deaths, Other Serious Adverse Events and Other Notable Adverse Events

The number and percentage of patients reported with an SAE during the treatment period will be summarized using MedDRA PT. A listing of SAEs will be provided.

The number and percentage of patients who permanently discontinued from study treatment due to an AE (including AEs that led to death) during the treatment period will be summarized using MedDRA PT. Events will be ordered by decreasing frequency.

5.13.3. Clinical Laboratory Evaluation

As described more fully in compound-level safety standards and in the laboratory-related PhUSE white papers (PhUSE 2013; PhUSE 2015), the clinical laboratory evaluations will be summarized as described in [Table KGBP.5.6](#). Hormone analytes are summarized/Plotted similarly.

Table KGBP.5.6. Summary Tables/Listing of Clinical Laboratory Evaluations

Summaries	Population
Box plots of observed values by visit	Safety
Box plots for change from baseline values by visit	
Change from baseline to last observations	Safety
Treatment-emergent abnormal high lab values (ie, patients shifting from a normal/low maximum baseline value to a high maximum postbaseline value) or abnormal low lab values (ie, patients shifting from normal/high minimum baseline value to a low minimum postbaseline value)	Safety
Shift tables showing the number of patients who shift from each category of maximum (minimum) baseline observation to each category of maximum (minimum) postbaseline observation. Here categories may be low, normal, or high with cut-offs defined in the compound-level safety standards.	Safety
Listing of abnormal findings for laboratory analyte measurements, including qualitative measures	Safety

5.13.4. Vital Signs and Other Physical Findings

As described more fully in compound-level safety standards and in the laboratory-related PhUSE white papers (PhUSE 2013; PhUSE 2015), vital signs will be summarized similarly to the clinical laboratory evaluation (Table KGBP.5.7). For vital signs, treatment-emergent low and high are based on a combination of a specified value and a change or percentage change as defined in the compound-level safety standards.

Table KGBP.5.7. Summary Tables/Figures Related to Vital Signs

Summaries	Population
Box plots for observed values by visit	Safety
Box plots for change from baseline values by visit	Safety
Tables with the number and percentage of subjects who shift from normal/high to low (ie, treatment-emergent low) and the number and percentage of subjects who shift from normal/low to high (ie, treatment-emergent high); the limits are defined in the compound-level safety standards	Safety

5.13.5. Immunogenicity

At the visits and times specified in the SoA, venous blood samples will be collected for the purpose of determining antibody production against lebrikizumab. To aid interpretation of these results, a blood sample for PK analysis will be collected at the same time points. All samples for immunogenicity should be taken pre-dose when applicable and possible. Instructions for the collection and handling of blood samples will be provided by the sponsor. The actual date and time (24-hour clock time) of each sample collection will be recorded. Immunogenicity samples will be stored at a facility designated by the sponsor and may be assessed at a later date using a validated assay designed to detect anti-drug antibodies (ADAs) in the presence of lebrikizumab at a laboratory designated by the sponsor. Samples may also be used for the development and control of an immunogenicity assay.

5.13.6. Special Safety Topics including Adverse Events of Special Interest

This section includes areas of interest whether due to observed safety findings, potential findings based on drug class, or safety topics anticipated to be requested by a regulatory agency for any reason. In general, potential AESI relevant to these special safety topics will be identified by 1 or more SMQs, by a Lilly-defined MedDRA PT listing based upon the review of the most current version of MedDRA, or by treatment-emergent relevant laboratory changes, as described below. Additional special safety topics may be added as warranted.

Unless otherwise specified, the AESI will be summarized for the safety population.

Full details of the search terms and rules for deriving AESI in each of the sections below are described in the compound-level safety standards along with information about the types of summaries and listings to be provided. In the event that the listing of terms or analysis changes for a special safety topic, it will be documented in the compound-level safety standards, which will supersede this document; it will not warrant an amendment to the individual study SAP.

5.13.6.1. Hepatic Safety

Hepatic labs include alanine aminotransferase (ALT) aspartate transaminase (AST), total bilirubin (TBL), and serum alkaline phosphatase (ALP).

Table KGBP.5.8. Summary Tables/Figure Related to Hepatic Safety

Summaries	Population
ALT and AST: The number and percentage of subjects with a measurement greater than or equal to 3 times (3X), 5 times (5X), and 10 times (10X) the performing lab ULN during the treatment period for all subjects with a postbaseline value and for subsets based on various levels of baseline value	Safety
TBL and ALP: The number and percentage of subjects with a measurement greater than or equal to 2 times (2X) the performing lab ULN during the treatment period will be summarized for all subjects with a postbaseline value and for subsets based on various levels of baseline value	
Plot of maximum postbaseline ALT vs. maximum postbaseline total bilirubin	Safety

Abbreviations: ALP = serum alkaline phosphatase; ALT = alanine aminotransferase; AST = aspartate transaminase; TBL = total bilirubin; ULN = upper limit of normal.

